9. CLINICAL INVESTIGATION PLAN

9.1. Investigational Medical Device

9.1.1. Identification

RGn550 is a reusable non-invasive class IIa electromedical device that is manufactured by REGEnLIFE and not CE-marked yet.

The current valid versions of RGn550's:

- Instructions for Use (IFU) is version 1 dated 07 April 2022
- Investigator brochure is version 1 dated 02 June 2022.

9.1.2. Description

[figure not shown]
A summarized description of RGn550 is provided below. For further details on the device, please refer to the IFU or investigator brochure.

9.1.2.1. Overall Description

RGn550 combines two technologies:

- **PhotoBioModulation (PBM)**, which involves exposure to directional low-power and high-fluence monochromatic or quasi-monochromatic light from the red to near-infrared wavelengths ($\lambda = 600\text{-}1,100\text{ nm}$) using lasers and Light Emitting Diodes (LEDs)
- **Static Magnetic Stimulation (SMS)**, which consists in the application of a static magnetic field using a neodymium magnet.

Further information on these two technologies is provided in section 9.2.1.2.

| | | |
|--------|---|--|
| RGnCON | Clinical Investigation Plan Version 2.0 - 11 August 2022 | |
|--------|---|--|

9.1.6. Training or Experience Needed to Use the Device

As mentioned in RGn550's investigator brochure:

A 2-hour theoretical and practical training, provided by REGEnLIFE's staff at the time RGn550 is delivered to the users, is required before using RGn550.

9.1.7. Specific Medical or Surgical Procedures Involved in the Use of the Device

No specific medical nor surgical procedures are involved in the use of RGn550.

| | |
|--|--------------|
| 2022.08.11_RGnCON_Prot_Final_V2.0_clean_public | Page 20 / 82 |
|--|--------------|

| | | |
|--------|---|---|
| RGnCON | Clinical Investigation Plan Version 2.0 - 11 August 2022 |  |
|--------|---|---|

9.2. Background, Rationale and Justification of the Clinical Investigation Design

9.2.1. Background

9.2.1.1. Concussion

9.2.1.1.1. Definition

Concussion is characterized by an immediate, transient and spontaneously reversible alteration of mental function, ranging from confusion to loss of consciousness, as a result of direct or indirect trauma with impulsive force to the head [1].

The following consensus definition was reached during the 5th international conference on concussion in sport held in Berlin in 2017 [2]:

Concussion is a traumatic brain injury induced by biomechanical forces. There are several common features that clinically define the nature of a concussive head injury:

- Concussion may be caused either by a direct blow to the head, face, neck or elsewhere on the body with an impulsive force transmitted to the head.
- Concussion typically results in the rapid onset of short-lived impairment of neurological function that resolves spontaneously. However, in some cases, signs and symptoms evolve over several minutes to hours.
- Concussion may result in neuropathological changes, but the acute clinical signs and symptoms largely reflect a functional disturbance rather than a structural injury and, as such, no abnormality is seen on standard structural neuroimaging studies.
- Concussion results in a range of clinical signs and symptoms that may or may not involve loss of consciousness. Resolution of the clinical and cognitive features typically follows a sequential course. However, in some cases symptoms may be prolonged.

The clinical signs and symptoms cannot be explained by drug, alcohol, or medication use, other injuries (such as cervical injuries, peripheral vestibular dysfunction, etc.) or other comorbidities (e.g., psychological factors or coexisting medical conditions).

It should be noted that the terms “mild Traumatic Brain Injury (TBI)” and “concussion” are often used interchangeably. In the broadest clinical sense, concussion is often defined as representing the immediate and transient symptoms of TBI. One key unresolved issue is whether concussion is part of TBI spectrum associated with lesser degrees of diffuse structural changes than are seen in severe TBI, or whether the concussive injury is the result of reversible physiological changes [2]. The term “concussion” is used throughout this document.

9.2.1.1.2. Physiopathology

As stated above, the concussion may be caused either by a direct blow to the head, face, neck or elsewhere on the body with an “impulsive” force transmitted to the head [2]. This blow can be received in various situations including falls, traffic accidents and sport practice [3, 4]. Sports at risk include hockey, American football, team sports, boxing and winter sports [1].

The pathogenesis of concussion has not been fully elucidated yet, but it is becoming increasingly clear that biomechanical forces lead to an energy crisis, neuroinflammation, cerebral blood flow changes, and pathological cascades, as detailed below and summarized in Figure 7 [5]:

- Biomechanical forces generate disruptions of neuronal cell membranes and axonal stretching, triggering indiscriminate flux of ions through previously regulated ion channels. This ions

imbalance causes neuronal depolarization, near-complete loss of electrochemical energy, and neuronal swelling.

- The adenosine triphosphate-dependent Na⁺/K⁺ pumps attempt to restore ionic homeostasis, and hyperglycolysis rapidly depletes energy stores, resulting in lactic acid buildup, and ultimately, the development of cerebral edema. In addition to the ionic flux, there is a hyperacute release of glutamate, the brain's primary excitatory neurotransmitter. Excessive glutamate receptor binding can activate calcium-dependent proteases and phospholipases, uncouple mitochondrial adenosine triphosphate synthesis, promote oxidative stress produce reactive oxygen species, deplete glutathione levels, and increase cellular energy demands.
- Concussion-induced disruption of the blood-brain barrier exacerbates the neuroinflammatory response mediated by immune cells, microglia, cytokines, and other inflammatory mediators. Blood-brain barrier dysfunction contributes to oxidative stress, inflammation, brain swelling, increased intracranial pressure, and ischemia.
- Shearing forces from a direct blow to the head or acceleration-deceleration transmitted through the neck interrupt axonal transport resulting in accumulation of transported materials in injured regions. Axonal dysregulation and accumulation of transport products lead to axonal swelling, secondary disconnection, and Wallerian degeneration (an active, cell-autonomous death pathway as a consequence of the axonal transport system's inability to deliver essential biosynthetic enzymes).

MIXED PATHOPHYSIOLOGY OF CONCUSSION

-Pender et al.

[figure not shown]

Figure 7: Physiopathology of concussion [5]

9.2.1.1.3. Symptoms

In the acute phase, concussion is an evolving injury with rapidly changing clinical signs and symptoms [2].

These symptoms can be categorized into [1–3, 6, 7]:

- Somatic symptoms, such as:
 - Headache
 - Vision changes including blurred vision, light sensitivity, difficulty reading and convergence dysfunction
 - Coordination disorders
 - Disturbance in balance
 - Insomnia
 - Somnolence
 - Drowsiness

| | | |
|--------|---|--|
| RGnCON | Clinical Investigation Plan Version 2.0 - 11 August 2022 | |
|--------|---|--|

- Cognitive impairment, such as:
 - Feeling like in a fog
 - Disorientation
 - Difficulty concentrating
 - Slowed reaction time
 - Loss of consciousness
 - Amnesia
 - Neurological deficit
- Emotional / behavioral changes such as:
 - Irritability
 - Lability

Altogether, this set of symptoms is called **concussion syndrome** [1, 6].

In adults, symptoms typically resolve in 10 to 14 days [2]. However, some may linger for weeks. Persistent post-concussion syndrome occurs when symptoms persist beyond 3 months [6].

Of note, well-trained and well-prepared sportspersons are thought to heal more rapidly [1, 4].

9.2.1.1.4. Complications

Although the short-term vital prognosis is very good (mortality < 1%), the functional prognosis in the mid- and long-term is more uncertain. Indeed, approximately 10-20% of the patients will have long-lasting effects [3].

The literature on neurobehavioral sequelae and long-term consequences of exposure to recurrent head trauma is inconsistent. However, reported potential long-term problems include [1, 2]:

- Cognitive impairment
- Depression
- Chronic traumatic encephalopathy (although a cause-and-effect relationship has not yet been demonstrated between chronic traumatic encephalopathy and concussion).

Of note, well-trained and well-prepared sportsperson are thought to have less complications. Interestingly, concussions have been reported to be more severe in sportswomen than sportsmen [1].

9.2.1.1.5. Management

Most consensus and agreement statements for managing concussion recommend that patients rest until they become symptom-free. Accordingly, prescribed rest is one of the most widely used interventions. The basis for recommending physical and cognitive rest is that rest may ease discomfort during the acute recovery period by mitigating concussion symptoms and/or that rest may promote recovery by minimizing brain energy demands following concussion. After a brief period of rest during the acute phase (24–48 hours) after injury, patients can be encouraged to become gradually and progressively more active while staying below their cognitive and physical symptom-exacerbation thresholds (i.e., activity level should not bring on or worsen their symptoms). It is reasonable for athletes to avoid vigorous exertion while they are recovering. The exact amount and duration of rest is not yet well defined in the literature and requires further study [2].

No pharmacological therapies are available specifically for concussion; therefore, medications for symptom management can be used (e.g., nonsteroidal anti-inflammatory drugs or amitriptyline for headaches, sleep aids, anxiolytics) [8].

| | | |
|--------|---|---|
| RGnCON | Clinical Investigation Plan Version 2.0 - 11 August 2022 |  |
|--------|---|---|

Sunglasses can be used in case of photophobia, and earplugs or noise-canceling headphones can be used in case of phonophobia [8].

9.2.1.1.6. Epidemiology and Burden

Epidemiological data suggest that 50 to 60 million people suffer from craniocerebral trauma in the world every year, including 60% to 95% of concussions. Men are more affected than women, with an overall relative risk close to 2 [3].

In France, there is a high prevalence of concussion: about 150,000 cases per year [3].

Of note, the OMS highlights that the incidence of concussions caused by rugby, American football, soccer and hockey are similar (from 0.6 to 0.8/1,000 athlete-game-hour) while, for combat sports, it is higher (e.g., 7-15/athlete-exposition in taekwondo) [4].

Due to its frequency and the significant risk of an unfavorable evolution (10-20% of cases), the concussion is considered a public health problem [3].

9.2.1.2. Photobiomodulation and Static Magnetic Stimulation

9.2.1.2.1. Photobiomodulation

PBM is a technique that was discovered more than 50 years ago, and that involves exposure to directional low-power and high-fluence monochromatic or quasi-monochromatic light from the red to near-infrared wavelengths ($\lambda = 600-1,100$ nm) using lasers or LEDs [9–11].

Of note, PBM also used to be called “low-level laser therapy” but the term “photobiomodulation” was chosen in 2015 as standard because the term “low” was deemed too vague and lasers are not absolutely required [9].

Photons generated by the lasers or LEDs are absorbed by molecules present in the cells, called photoacceptors. The molecule targeted by the light reaches an electronically excited state that temporarily changes its conformation and function, thereby triggering signaling pathways that affect cellular metabolism [9–11]. PBM is thought to stimulate healing, reduce inflammation, relieve pain, and prevent tissue from dying [9].

Transcranial PBM has been widely used in conditions such as wound healing, musculoskeletal pain, and arthritis, and is currently being tested for applications in aging-related neurocognitive decline, depression, and anxiety as well as various neurological disorders, including concussion [12].

In vivo studies have provided promising findings on the effects of transcranial PBM in concussion. Indeed, in animal models, transcranial PBM has been shown to:

- Reduce levels of pro-inflammatory cytokines [13, 14]
- Decrease levels of pro-apoptotic markers [15]
- Reduce the size of brain injury [16]
- Decrease neurological severity [17, 18]
- Improve neurological performance [16]
- Improve behavioral performance [15, 19].

Transcranial PBM was also evaluated across various devices at various parameters and treatment durations through several **clinical investigations** involving people with concussion or TBI, as fully described in the investigator brochure. Overall, transcranial PBM improved cognition, sleep disorders and quality of life and decreased headache, depression, anxiety and insomnia in these investigations. No side effects related to PBM were evidenced. However, since none of these investigations were

controlled nor randomized, there is a risk that such results were obtained because of coincidence only. Controlled randomized clinical investigations are necessary to reach conclusions [20].

9.2.1.2.2. Static Magnetic Stimulation

SMS is a non-invasive stimulation technique that consists of the application of a static magnetic field using a cylindrical neodymium magnet [21, 22].

Static magnetic fields have a constant intensity and direction over time, along with a frequency of 0 Hz. They are different from electromagnetic fields, which vary over time and are associated with induced electric currents [22, 23].

Non-invasive brain stimulation techniques, such as SMS, are becoming increasingly popular for treating a variety of neurological and neuropsychiatric disorders [22].

At the cellular level, **transcranial SMS** is thought to act primarily at the synapse and alter the function of membrane phospholipids and ion channels [22, 23]. It induces changes in voltage-gated calcium channels, intracellular calcium flow, and membrane depolarization [23].

At the systems level, transcranial SMS was demonstrated through **clinical investigations to modulate membrane excitability** for up to a few minutes after the end of stimulation:

- Application over the motor cortex was demonstrated to:
 - Reduce motor cortex excitability [21, 22, 24]
 - Reduce somatosensory cortex excitability (N33 component) [21]
 - Modulate intracortical excitability: enhanced facilitation and decreased inhibition [24].
- Application over the sensorimotor cortex was shown to reduce the somatosensory cortex excitability (N20 component) [21] and alter normal somatosensory processing [23]
- Finally, application over the visual cortex increases alpha oscillations and slows visual search abilities [21].

Although conventional non-invasive brain stimulation techniques have some undesirable side effects, such as itching, tingling, headache, and discomfort, these are not observed with transcranial SMS [21].

9.2.2. Rationale

Pre-clinical and clinical investigations were conducted by REGEnLIFE on the previous versions of RGn550 device (RGn500 and RGn530). Although some of these investigations relate to Alzheimer's Disease (AD) rather than concussion syndrome, they are presented below to:

- Testify that the device was previously used in animal models and humans
- Demonstrate that the device's use was safe
- Picture what could be the device performance in concussion syndrome, especially considering its effect on inflammation.

All these investigations are summarized below. For further details, please refer to RGn550's investigator brochure.

9.2.2.1. Pre-Clinical Investigation on RGn500 in Alzheimer's Disease

RGn500 was the first device used in a pre-clinical investigation involving animal models.

A **pre-clinical investigation** in an animal model of AD was conducted to evaluate RGn500's effects in a functional context [25].

The amyloid β 25-35 mouse model of AD was used: male Swiss mice were intracerebroventricularly injected with amyloid β 25-35 peptide. This model was chosen since it has been described as reproducing some of the features of AD. Indeed, this model has been repeatedly shown to result in neuroinflammation and reactive gliosis, pro-apoptotic caspases activity enhancement, oxidative stress, endogenously produced amyloid protein deposition, tau protein hyperphosphorylation, and increase of kinases, a reduction in the number of neurons measured in hippocampal pyramidal cell layers, loss of cholinergic neurons, and memory deficits.

Results showed a neuroprotective effect when treatment was applied both on the head and the abdomen. Protection was statistically significantly demonstrated through:

- Memory restoration
- Normalization of key markers of AD (amyloid β 1-42, pTau)
- Reduction of oxidative stress (lipid peroxidation)
- Normalization of apoptosis (Bax/Bcl2)
- Decrease in neuroinflammation.

When the treatment was localized only on the head or abdomen, RGn500 failed to yield beneficial effects.

Although this rodent model was far from reproducing the complexity of the physiopathological characteristics of AD dementia in humans, these results on RGn500 were promising, especially considering the extremely severe phenotype of amyloid β 25-35 mouse model of AD.

9.2.2.2. Pre-Clinical Investigations on RGn530 in Alzheimer's Disease

Following the preclinical investigation on RGn500, a new version of the device was created: **RGn530**.

Two pre-clinical investigations were conducted on RGn530 using the amyloid β 25-35 mouse model of AD.

[REDACTED]
[REDACTED] Results showed that, depending on the parameters used, RGn530 treatment significantly:

- Alleviated memory deficits (spatial working memory, contextual long-term memory)
- Reduced oxidative stress (lipid peroxidation)
- Decreased key markers of AD (amyloid β 1-42, pTau)
- Decreased neuroinflammation (TNF α).

In the second pre-clinical investigation, [REDACTED]
[REDACTED]

[REDACTED] Results showed full and highly significant reversal of memory deficits. No effects on the locomotor activity were observed.

9.2.2.3. Pre-Clinical Investigations to Validate RGn530's Security

Additional **pre-clinical investigations** were conducted on **RGn530** to validate its security. [REDACTED]
[REDACTED]
[REDACTED]
[REDACTED]
[REDACTED]
[REDACTED]
[REDACTED]

9.2.2.4. Pilot Clinical Investigation on RGn530 in Alzheimer's Disease

Following pre-clinical investigations on RGn530, the clinical safety and performance of the device on cognition in mild-to-moderate AD was evaluated for the first time in a **pilot clinical investigation**

[REDACTED]
[REDACTED]
[REDACTED]
[REDACTED]
[REDACTED]
[REDACTED]
[REDACTED]
[REDACTED]

A 10x10 grid of black and white bars of varying widths, representing a 2D barcode or matrix code. The pattern is composed of horizontal and vertical bars, with some bars being significantly thicker than others, creating a dense, binary-like structure.

In conclusion, this investigation proved RGn530 treatment feasibility and safety in mild-to-moderate AD patients. Although no statistically significant difference in ADAS-cog score after 8 weeks of treatment was observed, results evidenced encouraging performance trends to be evaluated in investigations with a larger sample size. Of note, statistical power was reduced due to the premature end of the investigation associated with the COVID-19 pandemic.

9.2.2.5. RGn550

Considering:

- The promising results of transcranial PBM in concussion that were published in the literature
- The effect of RGn500 on neuroinflammation demonstrated in the above-described pre-clinical investigation and the fact that a neuroinflammatory response is involved in concussion's physiopathology
- The good safety results obtained in AD patients in the pilot clinical investigation on RGn530

REGENLIFE decided to create a new version of the device, named **RGn550**, designed to be used in concussion syndrome.

[REDACTED]

[REDACTED]

[REDACTED]

[REDACTED]

Of note, REGENLIFE reviewed the differences between RGn530 and RGn550 and investigated their impact to determine whether pre-clinical investigations that validate RGn530's security [REDACTED] can validate RGn550's security as well. In this impact analysis [REDACTED] REGENLIFE concluded that these pre-clinical investigations indeed validate RGn550's security.

[REDACTED]

[REDACTED]

[REDACTED]

[REDACTED]

In this context, REGENLIFE wants to conduct a pilot clinical investigation on RGn550 to evaluate its safety and explore its performance in treating patients with acute concussion syndrome.

9.2.3. Justification of the Clinical Investigation Design

RGnCON is a prospective, comparative, randomized, simple-blinded, monocentric, pilot clinical investigation:

- A **prospective** design has been chosen since no data on the use of RGn550 in sportspeople suffering from acute concussion syndrome were previously collected.
- This investigation is **comparative**. It involves two parallel groups differing in terms of treatment frequency: half of the patients will be treated with 5 Hz, the other half with 10 Hz. This will allow to determine which frequency is optimal for the patient both in terms of safety and performance.
- Patients will be assigned to one of these two groups through **randomization** (1:1 ratio).
- Patients will not be aware of the group they were assigned to (**simple blinded**).
- A **monocentric** design has been chosen because RGnCON is a pilot investigation.

Various methodological aspects will prevent investigation bias:

- The presence of two groups will allow to take into consideration all confounding factors, apart from placebo effect.
- The unpredictable randomization will spread all known and unknown confounding factors (apart from placebo effect) within the two groups, resulting in comparable groups, and will prevent selection bias.

- Patients will be stratified based on gender (male/female) and concussion history (history/no history of concussion within 6 months prior to inclusion) as such parameters are known to influence current concussion symptoms and complications.
- The analysis will be performed in the Full Analysis Set (FAS) population without methods to replace missing data. However, some of the used models take into consideration missing data.

Of note, the following bias will remain present:

- The follow-up bias and evaluation bias since investigators will not be blinded
- The site effect since only one site will be recruited.

Nevertheless, the primary purpose of this investigation is to evaluate, for the first time, the safety of RGn550 in sportspeople suffering from acute concussion syndrome and explore its performance in this population. In case this investigation demonstrates RGn550's safety in this population, further investigation(s), using a double-blinding design versus sham, and involving more sites, will be conducted to demonstrate RGn550's safety and performance.

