9.4. Clinical Investigation Objectives and Hypotheses

As a pilot investigation, the objective of RGnCON is to demonstrate RGn550's safety and explore its performance in treating adult sportspeople with acute concussion syndrome.

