9.5.3. Conduct

9.5.3.1. Patient Inclusion

It is planned to include 50 patients in this investigation (refer to section 9.6.1 for sample size justification).

Based on this number and considering that the site estimated that it would be able to include approximately 3 patients per week, a 4-month inclusion period is planned: from September 2022 to December 2022.

The recruited site will be the Hôpital européen Georges-Pompidou located in Paris. The principal investigator will be a neurologist specialized in sport concussions and the coinvestigator will be a sport physician and posturologist.

In current clinical practice, following a shock, a sportsperson with obvious signs of concussion is examined by a physician within 72 hours after the shock to establish the diagnosis of concussion. For example, in the context of professional rugby, the French federation's regulation requires to follow HIA protocol immediately after the shock and the appearance of such signs. This protocol, composed of three steps, is performed by a physician within 48 hours after the shock:

- Step 1: Assessment during the match using HIA1
- Step 2: Post-match assessment, the same day, using HIA2
- Step 3: 36-48 hours post-injury assessment using HIA3.

The subjects of RGnCON investigation will be identified among sportspersons examined by the principal investigator within 72 hours after the shock. They will be included if they meet eligibility criteria and agree to participate in the investigation. Of note, HIA3 is mentioned in the eligibility criteria as the diagnostic tool for concussion. Indeed, as the principal investigator is the referring neurologist for a lot of rugby clubs and several sports federations, it is expected that most subjects will be professional rugby players for whom this protocol is implemented in current clinical practice. Nevertheless, subjects practicing other sports may be included as well if they have a diagnosis of concussion confirmed by the HIA3, meet the eligibility criteria and agree to participate.

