9.6. Statistical Considerations

9.6.1. Sample Size Justification

For a sample size of 50 patients, the probability of observing at least one ADE will be 0.87 considering a probability of ADE of 0.04. The sample size calculation was performed with SAS® v9.4.

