9.6.3. Statistical Analysis

Full details related to statistical analysis will be provided in the Statistical Analysis Plan.

The statistical analysis will be performed using SAS® Viya v9.4 (or a more recent version).

The global significance level (type I error rate) will be set at $\alpha = 0.05$ (two-sided). Adjustment for multiplicity is not applicable for the primary endpoint and no adjustment for multiplicity is planned for secondary endpoints.

Continuous data will be described by the number of missing data, number of data analyzed, mean, standard deviation, median, Q1, Q3, minimum, maximum.

Categorical data will be described by the number of missing data, frequencies and percentages of patients in each modality. The percentage of patients will be calculated once missing data are excluded from the denominator.

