## 8.4. Safety analysis

### 8.4.1. Analysis of the primary safety endpoint: proportion of patients with at least one ADE after use of RGn550

The proportion of patients with at least one ADE after use of RGn550 in acute concussion syndrome, either at a frequency of 5 or 10 Hz, will be calculated along with its 95% confidence interval (using exact Clopper-Pearson method). This analysis will be performed on the FAS population, by treatment groups and overall.

The following template will be used.

	RGn550 5Hz N=xx	RGn550 10Hz N=xx	Total N=xx
At least one ADE			
Non-missing	xx	xx	xx
Yes [n (%) 95% CI]	xx (xx.x) xx.x ; xx.x	xx (xx.x) xx.x ; xx.x	xx (xx.x) xx.x ; xx.x
No [n (%) 95% CI]	xx (xx.x) xx.x ; xx.x	xx (xx.x) xx.x ; xx.x	xx (xx.x) xx.x ; xx.x
missing	xx	xx	xx

Note: a lost to follow-up rate of 10% is anticipated. If this rate is higher, an analysis of the primary endpoint using percentage of patient-years will be considered.

Note: at the time of writing this SAP version, a data review has been performed showing that the lost-to-follow-up rate is 0%.

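### The protocol says the two-arm design will determine the optimal frequency for safety, but no between-arm ADE contrast is planned and the sample size was not set for one

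*Protocol*

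**What the plan says.** Protocol 9.2.3 calls the investigation comparative and explains that "half of the patients will be treated with 5 Hz, the other half with 10 Hz". It then gives the purpose of the two groups: "This will allow to determine which frequency is optimal for the patient both in terms of safety and performance".

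The safety objective and analyses are narrower:

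- The primary objective (Protocol 9.4.1) is to evaluate how often ADEs occur when the device is used at either frequency. It states no comparison.
- The primary analysis (Protocol 9.6.3.1, SAP 8.4.1) is the proportion of patients with any ADE, with an exact Clopper-Pearson interval. SAP 8.4.1 adds: "This analysis will be performed on the FAS population, by treatment groups and overall". Its table has columns for 5 Hz, 10 Hz and Total only.
- The secondary safety table (SAP 8.4.2) has the same three columns. The tables by system organ class and preferred term (SAP 8.4.3 and 8.4.4) are counts and percentages.
- SAP section 10, which lists changes from the protocol, adds no between-arm safety contrast.

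On size, Protocol 9.5.3.1 says "It is planned to include 50 patients in this investigation". Protocol 9.6.1 says that for this number "the probability of observing at least one ADE will be 0.87", at an assumed ADE probability of 0.04. It gives no rate per arm, no difference of interest and no rule for choosing a frequency.

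**The concern.** The stated reason for having two arms includes finding the better frequency on safety, yet the safety analysis never estimates how the arms differ. A reader who wants an answer must compare two wide intervals reported side by side, and these do not show the precision of the difference.

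Protocol 9.2.3 foresees further sham-controlled investigations. If one frequency is carried forward because this trial was said to have determined the safer one, the choice could rest on a difference of one or two patients.

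The SAP treats performance differently. In 8.5.1.1 the template for continuous endpoints has a difference column with a confidence interval and p-value, and the template for categorical endpoints has 10 Hz versus 5 Hz odds ratios. The gap is specific to safety.

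**Working it through.** **Inputs.** Planned total 50 (Protocol 9.5.3.1); 1:1 allocation (9.2.3), so about 25 per arm; ADE probability 0.04 (9.6.1); two-sided alpha 0.05 (9.6.3). Protocol 9.6.3.1 anticipates 10% loss to follow-up, but SAP 8.4.1 reports 0% at data review, so 25 is not reduced. Every rate other than 0.04 below is an assumption, because the documents give no other rate and the anticipated ADE content is redacted.

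**Step 1: the plan's own figure.** P(at least one ADE) = 1 − (1 − p)^n. With n = 50 and p = 0.04: 1 − 0.96^50 = 0.870. This reproduces the stated 0.87.

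**Step 2: the same quantity in one arm.** 1 − 0.96^25 = 0.640.

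**Step 3: precision of one arm.** With no events, the upper two-sided Clopper-Pearson limit is 1 − 0.025^(1/n): 13.7% for 0/25 and 7.1% for 0/50. For 1/25 the interval is 0.1% to 20.4%; for 3/25 it is 2.6% to 31.2%.

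**Step 4: what a comparison of 25 with 25 could separate.** Exact Fisher power is the sum, over all count pairs (a, b) with two-sided Fisher p ≤ 0.05, of Bin(a; 25, p1) × Bin(b; 25, p2). With p1 = 0.04:

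| Assumed rate in the other arm | Exact Fisher power |
|---|---|
| 8% | 0.006 |
| 12% | 0.035 |
| 16% | 0.109 |
| 20% | 0.230 |
| 30% | 0.605 |
| 36% | 0.781 |
| 38% | 0.826 |

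Power first reaches 0.80 at about 37%. In terms of counts, 0 versus 6 patients gives p = 0.022 and 1 versus 7 gives p = 0.049. Neither document plans this test; it is used only to show how much information 25 per arm carries.

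**Step 5: ranking the arms by raw counts.** If the true rates were 4% and 8%, the arm with the lower true rate would show fewer affected patients 61% of the time, tie 21% and show more 18%. The arm with the higher rate would therefore look equal or better in about 39% of trials.

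**Step 6: what the missing estimate would look like.** Take 2/25 versus 1/25 as an example. The Wilson intervals are 2.2% to 25.0% and 0.7% to 19.5%, and the difference is 0.08 − 0.04 = 0.04. Newcombe limits:

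- Lower: 0.04 − √[(0.080 − 0.022)² + (0.195 − 0.040)²] = −0.126
- Upper: 0.04 + √[(0.250 − 0.080)² + (0.040 − 0.007)²] = 0.213

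The interval, −12.6% to +21.3%, is compatible with either arm being the safer one.

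**The case against.** The strongest reply is that Protocol 9.2.3 limits its own claim. It closes by saying that the main purpose is a first look at safety with performance explored, and it leaves demonstration to later double-blind, sham-controlled work at more sites. The sentence about the optimal frequency is design rationale, not an objective, hypothesis or decision rule, and the planned analysis answers the primary objective as written. This stands, and it makes the point one of matching a claim to an analysis. It does not remove the mismatch, because the sentence says determine and names safety.

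A second reply is that per-arm counts and intervals are already planned for ADEs overall and by severity, AEs, device deficiencies, SAEs and SADEs, so anyone can work out a difference. That is true, and the interval will be wide. Showing that width is the reason to print it: it discourages ranking the arms on small counts.

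A third reply is that the comparison rates in the power table are not the sponsor's. This is also right. They are assumptions, and a very large gap (about 4% versus 37%) would be detectable.

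Three stronger readings are tempting, but the documents do not support them:

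- *The 0.87 is wrong or misleading.* It is arithmetically correct, is labelled for 50 patients and fits the overall analysis. Nothing presents it as a per-arm or comparative figure.
- *The whole sentence on optimal frequency is unsupported.* For the modelled performance endpoints, SAP 8.5.1 plans between-arm contrasts. Only the safety half lacks one.
- *The general aim of showing the device's safety in Protocol 9.4 adds to the problem.* That aim concerns the device and says nothing about comparing frequencies.

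**Conclusion.** The concern holds for safety only. Protocol 9.2.3 claims that the design will settle which frequency is optimal on safety, neither document plans a between-arm ADE contrast, and the sample size was set for detecting any ADE in the pooled 50 patients.

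With about 25 per arm and the one documented rate of 4% in one of them, differences near the planning rate could not be separated: illustrative power is 0.006 to 0.23 against 8% to 20%, and reaches 0.80 only near 37%. This rests on equal arms of 25, on 4% in the lower arm and on assumed rates in the other.

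The primary objective, the per-arm and overall proportions and the 0.87 are unaffected. The point is worth correcting because the claim could shape which frequency is taken forward, but it does not undermine the trial's main analysis.

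**What to change.** - **SAP 8.4.1:** add a column with the 10 Hz minus 5 Hz difference in the proportion of patients with any ADE and its 95% confidence interval (for example Newcombe), labelled exploratory and with no p-value needed.
- **SAP section 10:** list this contrast as an addition made after the data review. SAP version 2.0 of 3 August 2023 already draws on data review minutes dated 18 July 2023, so the contrast cannot be presented as specified before that review.
- **Protocol 9.2.3 and the conclusions of the report:** replace the safety part of the claim with wording such as *give exploratory estimates of the difference between frequencies*. If the protocol is no longer to be amended, the wording in the report matters most.
- **Optional, Protocol 9.6.1:** state 0.64 per arm beside 0.87 for all 50.

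The cost is one table column, one entry in the list of changes and a few words. It needs no extra patients or data. The cost in standing is that the added contrast must carry its post-review label.
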